2.3. Exploratory Objective

Table 2-3 Exploratory Objective and Outcome Measures

Exploratory Objectives	Outcome Measures
To collect and store blood samples for potential future measurement of cyclosporine and/or rifampicin plasma levels.	If samples are analysed: cyclosporine and rifampicin plasma concentrations.
To collect blood and urine samples for additional clinical chemistry and urinalysis.	Collected on Days 1, 2 and 3 in Treatment Period 1.
Exploratory data will not form part of the CSR and will study.	not be included in the tables, figures or listings of this

Refer to Section 10.2 for PK variables and Section 6.3 for safety variables.

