Blood sampling for analysis of verinurad, M1, M8, allopurinol and oxypurinol plasma concentrations			Xi	Xi		Xi		Section 6.4.2
Exploratory blood sampling for analysis of cyclosporine blood concentrations				Xi				Section 6.4.2
Exploratory blood sampling for analysis of rifampicin plasma concentrations						Xi		Section 6.4.2

Abbreviations: AE = Adverse event; BMI = Body mass index; ECG = Electrocardiogram; FSH = Follicle stimulating hormone; HBc = Hepatitis B core; HIV = Human immunodeficiency virus; HLA-B = Human leukocyte antigen B; SAE = Serious adverse events;

Study Assessments	Visit 1		Visit	2	Vis	it 3	Visit 4	Corresponding Section in
	Screening	Treat Peri		Treatment Period 2	Treat Peri		Follow-up or Early Termination	Protocol
	Day -28 to -2	Day -1	Days 1 to 5	Days 1 to 5	Day -1	Days 1 to 5	7-14 days after last verinurad dose	

- ^a Subjects will be allowed to leave (discharged from) the clinical unit after the last PK sample is taken at 96 hours after dosing (Day 5).
- b Occurs on Day 1, in each Treatment period (considered as the 0 hour time point)
- Subjects will be contacted within 24 hours before a scheduled visit to the Clinical Unit to confirm that no signs and/or symptoms of COVID-19 are present and that no subject had any contact with a known SARS-CoV-2 positive tested person within the last 14 days. In the case that a subject confirms signs and/or symptoms or has had contact with a SARS-CoV-2 positive person, the visit will be canceled and the reason for the cancellation will be appropriately documented.
- d Only SAEs will be recorded during the Screening period and on Day -1 Treatment Period 1 (Visit 1)
- ^e Blood pressure, pulse rate (supine) and temperature (tympanic) will be taken at pre-dose and 1.5, 4, and 6 hours after dosing on Day 1 and on Days 2, 3, 4 and 5 in each Treatment Period.
- In Treatment Period 1, urine samples and blood for clinical chemistry will be collected on Days 1, 2 and 3. Urine samples will include only the measurement of sodium, creatinine, lactic acid, potassium, aldosterone and pH. Blood samples will include only the measurement of creatinine, cystatin-C and sodium.
- Blood for haematology will be collected on Day 3 only.
- ^h A full physical exam will occur at the Screening and Follow-up Visits. A brief physical exam will occur on Day -1 and Day 3 in each Treatment Period.

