The Investigator will assess causal relationship between investigational product and each AE, and answer "yes" or "no" to the question "Do you consider that there is a reasonable possibility that the event may have been caused by the investigational product?"

For SAEs, causal relationship will also be assessed for other medication, any additional drug and study procedures. Note that for SAEs that could be associated with any study procedure the causal relationship is implied as "yes".

A guide to the interpretation of the causality question is found in Appendix A of this CSP.

Adverse Events Based on Sign and Symptoms

All AEs spontaneously reported by the subject or reported in response to the open question from the study personnel: "Have you had any health problems since you were last asked?", or revealed by observation will be collected and recorded in ClinBaseTM.

When collecting AEs, the recording of diagnoses is preferred (when possible) to recording a list of signs and symptoms.

However, if a diagnosis is known and there are other signs or symptoms that are not generally part of the diagnosis, the diagnosis and each sign or symptom will be recorded separately.

Adverse Events Based on Examinations and Tests

The results from protocol-mandated laboratory tests, vital signs, ECGs and other safety assessments will be summarised in the CSR.

Deterioration as compared to baseline in protocol-mandated laboratory values, vital signs, ECGs and other safety assessments should therefore only be reported as AEs if they fulfill any of the SAE criteria, is clinically significant according to the Investigator judgment, or are the reason for discontinuation of treatment with the investigational product.

If deterioration in a laboratory value or vital sign is associated with clinical signs and symptoms, the sign or symptom will be reported as an AE and the associated laboratory result or vital sign will be considered as additional information.

Wherever possible the reporting Investigator should use the clinical, rather than the laboratory term (eg, anaemia versus low haemoglobin value).

In the absence of clinical signs or symptoms, clinically relevant deteriorations in non-protocol-mandated parameters should be reported as AE(s).

Any new or aggravated clinically relevant abnormal medical finding at a physical examination as compared with the baseline assessment will be reported as an AE.

Hy's Law

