10.1.2. Laboratory Assessments

Haematology and clinical chemistry values will be listed by subject and time point including changes from baseline and repeat/unscheduled measurements. Summary tabulations including absolute value and changes from baseline will be presented by treatment period and time point for the safety analysis set. The baseline for the measurements will be the last assessment performed prior to dosing in Treatment Period 1. Changes from baseline will be calculated and presented for all post-baseline time points including the Follow-up Visit. Shift tables will also be presented.

Any laboratory parameters with results from the laboratory given as "< xx" or ">xx" in the database will be imputed with the absolute value of the number without the sign (eg, < 2.2 will be imputed as 2.2) for the descriptive statistics and changes from baseline.

The listings will include the following information: test name, date of measurement, reference range, result and flags for any measurements that are outside the reference range (eg, AstraZeneca, program, or laboratory ranges). Clinical laboratory data will be reported in System International units in the CSR.

Additional listings will be presented for the following:

- Urinalysis (macroscopic and microscopic, if applicable)
- The results of viral serology and the drugs of abuse and alcohol screen will not be listed in the CSR

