11.2.8. Pharmacodynamics – Not Applicable

11.2.9. Pharmacogenetics – Not Applicable

11.2.10. Exploratory Data

Results from exploratory data will not form part of the CSR and will not be included in the tables, figures or listings of this study.

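### The Period 1 Days 1-3 serum creatinine, cystatin-C and sodium are classed as exploratory and kept out of the CSR, while the laboratory and adverse-event rules assume they are reported

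*Combined protocol and SAP*

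**What the plan says.** **Schedule.** Table 3-1 (Section 3.1) places clinical chemistry under clinical laboratory evaluations. Footnote f adds: "In Treatment Period 1, urine samples and blood for clinical chemistry will be collected on Days 1, 2 and 3". It limits the blood analytes to creatinine, cystatin-C and sodium, and does not say whether the Day 1 sample precedes dosing. The chemistry row is not marked exploratory. The cyclosporine and rifampicin sampling rows are so marked, both here and in Table 7-1.

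**Exploratory classification.** Table 2-3 (Section 2.3) gives as an exploratory objective: "To collect blood and urine samples for additional clinical chemistry and urinalysis". Its outcome measure reads: "Collected on Days 1, 2 and 3 in Treatment Period 1". Section 11.2.10 then says: "Results from exploratory data will not form part of the CSR and will not be included in the tables, figures or listings". The synopsis and the note to Table 2-3 say the same.

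**Safety rules.** Section 6.3 names clinical chemistry among the safety variables, and Section 11.2.5 puts all safety data in the listings. Section 10.1.2 says: "Changes from baseline will be calculated and presented for all post-baseline time points including the Follow-up Visit". It defines the baseline as follows: "The baseline for the measurements will be the last assessment performed prior to dosing in Treatment Period 1".

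**Adverse-event rule.** Section 6.3.1.4 begins: "The results from protocol-mandated laboratory tests, vital signs, ECGs and other safety assessments will be summarised in the CSR". It then draws a consequence for laboratory deterioration and similar findings: "safety assessments should therefore only be reported as AEs if they fulfill any of the SAE criteria", or if the investigator judges them clinically significant, or if they are the reason for stopping treatment.

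**The concern.** The same samples fall under two reporting instructions. A programmer who follows Section 11.2.10 leaves them out of every table and listing. One who follows Sections 10.1.2 and 11.2.5 includes them.

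The conflict matters most through Section 6.3.1.4. That section accepts a narrow adverse-event rule for laboratory changes because the values will be visible in the CSR anyway. For the Period 1 Days 1-3 samples, Section 11.2.10 removes that ground and leaves the narrow rule in place. Section 6.4.1.1 provides a separate report for cyclosporine and rifampicin concentrations, if they are analysed. No such route is stated for this chemistry.

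Section 3.3 calls creatinine elevation the main toxicity concern with verinurad monotherapy in healthy subjects and describes it as mostly transient. Samples taken soon after a dose are those best placed to show a transient rise, and these are the ones excluded.

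**Working it through.** **Step 1. Confirm which chemistry samples exist.** Counts from Table 3-1 against the blood budget in Table 7-1:

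| Sample | Table 3-1 | Table 7-1 |
|---|---|---|
| Full chemistry | Screening, Period 1 Day -1, Period 3 Day -1, Follow-up = 4 | 4 x 7.5 = 30.0 mL |
| Reduced chemistry | Period 1 Days 1, 2, 3 = 3 | 3 x 2.6 = 7.8 mL |

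The total in Table 7-1 is reproduced: 18.9 + 30.0 + 7.8 + 3.0 + 2.6 + 153.0 + 102.0 + 17.0 + 17.0 = 351.3 mL. The budget has no room for another scheduled chemistry sample, so the blank chemistry cells for Days 1-5 of Periods 2 and 3 are real.

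**Step 2. Place the samples relative to the doses.** The only scheduled chemistry in the 96 h after any dose is the Period 1 Days 1-3 set. The next scheduled chemistry after the cyclosporine combination is Period 3 Day -1. That is at least about 14 - 1 = 13 days after the dose, given the 14-day minimum between doses. After the rifampicin combination it is the Follow-up Visit, at 7-14 days.

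**Step 3. Count the scheduled post-dose serum creatinine values.** Assume that all 14 enrolled subjects complete.

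- Period 1, if the Day 1 sample is pre-dose: 14 x 2 = 28 (Days 2 and 3).
- Period 1, if the Day 1 sample is post-dose: 14 x 3 = 42.
- Later values (Period 3 Day -1 and Follow-up): 14 x 2 = 28.

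Share left out of the CSR if Sections 2.3 and 11.2.10 are followed:

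- Day 1 pre-dose: 28 / (28 + 28) = 28/56 = 50%.
- Day 1 post-dose: 42 / (42 + 28) = 42/70 = 60%.

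Per subject the shares are 2/4 and 3/5, so they do not depend on the number of completers. In either case every scheduled value within 96 h of a dose is among those omitted.

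**Step 4. Follow one value through the rules.** Take a Period 1 Day 2 creatinine rise that is not serious, is judged not clinically significant, does not stop treatment and prompts no repeat. Section 6.3.1.4 does not make it an adverse event, because its value is expected in the CSR. Section 11.2.10 keeps that value out of the CSR. Unless the sponsor's medical review picks it up (Section 6.3.1.3), it appears nowhere.

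**Step 5. Check the baseline.** If the Day 1 sample is pre-dose, Section 10.1.2 read literally makes it the baseline for the three analytes, and Section 11.2.10 keeps it out of the tables. If it is post-dose, or if exploratory samples do not count, the baseline is the Day -1 panel. The text does not settle which applies.

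**The case against.** The strongest defence is that the exclusion is deliberate. The synopsis and Sections 2.3 and 11.2.10 agree with one another, Table 2-3 names the exact days, and a specific exclusion normally overrides general rules. The general rules are framed around safety data, and footnote f describes a narrow panel added only to the reference period. This explains how the exclusion can be intended. It does not repair Section 6.3.1.4, whose stated ground then fails for these samples, and it leaves Table 3-1 showing them unlabelled beside ordinary safety chemistry.

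A second defence is that important findings would still surface. That is right. Serious or clinically significant rises, and those leading to discontinuation, are adverse events. Section 6.3.1.3 provides a sponsor medical review of laboratory data. Appendix D calls for repeat creatinine after a rise of at least 1.5-fold from baseline, and unscheduled safety values are listed under Section 11.2.5. A reader might infer that the plan could hide important renal events; the documents do not support that.

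A reader might also infer that the lack of scheduled chemistry soon after the two combination doses contradicts the combination safety objective. It does not. Table 2-2 names clinical laboratory assessment without fixing its timing. Haematology is drawn on Day 3 of every period, and full chemistry follows later. This is a monitoring choice that contradicts no other section.

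The protocol also gives reasons to expect few events: no apparent relation of creatinine rises to dose, mitigation by allopurinol and hydration, and no rise of at least 1.5 times baseline in the verinurad plus allopurinol study in healthy Asian and Chinese subjects (Sections 1.1, 3.3 and 3.3.1). These lower the likely yield of the samples. They do not decide how the results are reported.

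**Conclusion.** The reporting conflict holds. Sections 2.3 and 11.2.10 cannot be followed together with Table 3-1 and Sections 6.3, 10.1.2 and 11.2.5 as written, and they remove the ground given in Section 6.3.1.4. The consequence is limited: the CSR would lack the listing and summary of 50% to 60% of scheduled post-dose creatinine values, including all of those within 96 h of a dose. The range rests only on whether the Day 1 sample is pre- or post-dose; the counts assume 14 completers.

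The baseline question should be cleared up in the same edit, but it is conditional on an unstated sampling time and is not a separate error. No estimate is offered of how many rises would go unreported, because the documents give no rate that applies to a single verinurad dose with allopurinol. The primary PK objectives are unaffected. Severity is minor to should-fix: the effect is modest, but it touches the stated main toxicity concern and costs almost nothing to put right.

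**What to change.** 1. Treat the Period 1 Days 1-3 serum creatinine, cystatin-C and sodium as safety data, and list and summarise them under Section 10.1.2. Amend Sections 2.3 and 11.2.10, and the matching synopsis text, to agree with Table 3-1 and Sections 6.3, 6.3.1.4, 10.1.2 and 11.2.5.
2. In the same edit, state whether the Day 1 sample is before or after dosing, so that the Section 10.1.2 baseline for these analytes is defined.
3. In the CSR, when stating the combination safety conclusion, note that no chemistry was scheduled in the 96 h after the two combination doses.

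The cost is a few sentences and a little more programming on data already to be collected. No change to the sampling schedule is proposed.

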3.1.1. Order of Assessments

It is important that PK sampling occurs as close as possible to scheduled time. In order to achieve this, other assessments scheduled at the same time may be initiated prior to the time point. The sequence at a particular time point is:

- 1 Vital signs (systolic and diastolic blood pressure, pulse rate and tympanic temperature)
- 2 PK blood sampling (will be drawn at the specified time points)
- 3 Safety laboratory blood sampling

Tolerance windows for the assessments will be detailed in the WAD.

3.1.2. End of Study

The end of study is defined as the last subject's last visit to the Clinical Unit.

3.1.3. Expected Duration of the Study

Each subject will be involved in the study for approximately 9 weeks and have approximately 4 study visits.

3.2. Rationales for Study Design and Dose Selection

3.2.1. Rationale for Study Design

This study has been designed to quantify the effects on verinurad PK when co-administered with cyclosporine, a broad transporter inhibitor, or rifampicin, an OATP1B1/3 inhibitor when given as a single dose.

A fixed-sequence design allows to determine whether cyclosporine or rifampicin affects the PK of verinurad. Verinurad is given in combination with allopurinol, since verinurad is developed as a fixed dose combination with allopurinol. This design is consistent with regulatory guidelines for drug interaction studies [11].

The 14-day washout period between Treatment Periods 2 and 3 dosing, is considered sufficient to avoid carry-over effects between Treatment Periods 2 and 3. The 7-14 days washout period between rifampicin administration and the Follow-up Visit is also considered a sufficient time period [18].

The PK sampling time points in all periods (up to 96 hours) are based on the plasma half-lives of the IMP as well as previous experience in assessing PK profiles of verinurad, allopurinol and their metabolites [1, 16].

3.2.2. Dose Rationale

A single dose of 7.5 mg verinurad, formulated as an extended release capsule (ER8) is selected for this study. This is the middle dose currently tested in a Phase 2b study. The AUC and Cmax of verinurad increases in a dose proportional manner after administration of single doses of 4.5 to 12 mg ER8 verinurad capsule. Multiple dosing of 24 mg ER8 verinurad once daily doses, and single doses of 40 mg verinurad as immediate release tablets, have been assessed previously in healthy volunteers and been found to be well tolerated.

A single dose of 300 mg of allopurinol was selected because it is the intended clinical dose in the verinurad+allopurinol fixed-dose-combination.

A single dose of 600 mg cyclosporine reflects daily doses in transplant patients and has been used in similar drug-drug interaction studies in the past [12, 13].

A single dose of 600 mg rifampicin is the highest daily recommended dose and has been used for both single and multiple dosing in drug-drug interaction studies in the past [14, 15].

3.3. Risk-benefit Assessment

There are no direct benefits for the subjects participating in this study. However, study-related health assessments are provided without costs for the subjects. The major risks for subjects who participate in the study will come from IMP administration. In addition, there might be a slight risk of infection or bruising that might occur after insertion of an intravenous cannula for frequent blood sampling.

The main toxicity concern noted with verinurad monotherapy in healthy subjects is creatinine elevations $>1.5 \times$ baseline which occurred in 1.7% of healthy subjects. A change from baseline of ≥ 0.3 mg/dL was reported for 6.8% of all subjects. There was no apparent relationship between sCr elevation and dose of verinurad. The creatinine elevations were primarily transient, and often resolved despite continued dosing with verinurad. This risk is mitigated by combining verinurad with an XOI, excluding subjects with high uric acid and mandating hydration. Further information is provided in the IB [1].

In previous studies, verinurad combined with allopurinol was well tolerated and associated with acceptable side effects. Most AEs were minor and not related to treatment.

Allopurinol is an approved XOI. Most common AEs identified in the prescribing information are rash and blood thyroid-stimulating hormone increased. Allopurinol hypersensitivity reactions can manifest in many different ways, including maculopapular exanthema, hypersensitivity syndrome (also known as drug rash with eosinophilia and systemic symptoms [DRESS]) and SJS/TEN. The human leukocyte antigen B (HLA-B)*58:01 allele has been shown to be associated with increased risk of developing allopurinol-related hypersensitivity

syndrome and SJS/TEN. The frequency of the HLA-B*58:01 allele varies widely between ethnic populations: up to 20% in the Han Chinese population, 8 to 15% in the Thai population, about 12% in the Korean population and 1 to 2% in individuals of Japanese or European origin. At the Screening Visit, the subject's HLA-B*58:01 status will be tested and carriers of HLA-B*58:01 will be excluded [16].

Overall, the study has been designed to minimize the risks to participating subjects by excluding subjects at high risk of AEs and by applying appropriate safety monitoring of recruited study subjects. This is a single dose study and subjects will only be exposed to 1 dose of each treatment (verinurad+allopurinol, verinurad+allopurinol+cyclosporine and verinurad+allopurinol+rifampicin). The dose selected has been carefully considered in light of the target subject population. The potential benefits of developing a new treatment for chronic kidney disease with hyperuricemia, therefore, outweigh the limited risks to the subjects exposed to verinurad and allopurinol single doses in this study.

3.3.1. Adverse Events, Contraindications and Warnings of Verinurad

Verinurad has been studied in healthy subjects, patients with gout and renally-impaired patients. In total, 849 subjects have received verinurad in 11 Phase I and 7 Phase II clinical studies (data as of 01 Nov 2019).

Safety in healthy subjects was assessed in a pooled analysis of 8 Phase I (Studies 101, 103, 104, 105, 106, 110, 111, and 112) and in a single Phase I study (D5495C00006). A summary of information on clinical safety findings in healthy subjects is provided below; further details are available in the IB [1].

Adverse Events

The 8 pooled Phase I studies collectively enrolled 293 male subjects, treated at doses ranging from 5 to >15 mg; 94.5% of the subjects completed the planned treatment. Overall, 86 subjects (29.4%) experienced AEs. The incidence of AEs was similar among the pooled verinurad groups and pooled placebo groups. The most common AE was headache, which occurred in 12 subjects (4.1%). There was no apparent relationship between the incidence of these AEs and verinurad dose. Most AEs were RCTC toxicity Grade 1. Only 2 AEs had an RCTC toxicity >Grade 2, consisting of Grade 3 blood creatinine increased and Grade 3 tooth infection, both reported in subjects treated with verinurad doses ranging from 5 to <10 mg. There were no SAEs. Three subjects withdrew from the study due to AEs: 2 subjects who had received verinurad 5 mg (dehydration and influenza, respectively) and 1 subject who had received verinurad 15 mg and experienced urticaria.

Study D5495C00006 was a double-blind safety and PK study in healthy Asian and Chinese subjects who were randomised to receive verinurad + allopurinol or placebo. No deaths or

SAEs were reported in the study and no subject discontinued IMP due to an AE. All AEs reported on IMP were mild in intensity.

Laboratory Evaluations

In the pooled analysis of the 8 Phase I studies, sCr elevations $\geq 1.25 \times$ baseline and $\geq 1.5 \times$ baseline were reported for 13.7% and 1.7% of subjects, respectively. A change from baseline ≥ 0.3 mg/dL was reported for 6.8% of all subjects. There was no apparent relationship between sCr elevation and dose of verinurad. Furthermore, 18.4% of all subjects treated with verinurad experienced ALT elevations $\geq 1.5 \times$ baseline, 5.1% experienced elevations $\geq 2.0 \times$ baseline, and 2.0% experienced elevations $\geq 3.0 \times$ baseline. There was no clear relationship with dose. Aspartate aminotransferase elevations $\geq 1.5 \times$ baseline were reported for 6.1% of all subjects, while < 1.5% of subjects experienced AST elevations ≥ 2.0 or $\geq 3.0 \times$ baseline.

In Study D5495C00006, no subjects on verinurad + allopurinol had an elevation >3.0 × ULN for ALT or AST or >2.0 × ULN for total bilirubin. No sCr elevation \ge 1.5 × baseline was observed in the study.

Vital Signs, Physical Findings, and Other Observations

In the 9 Phase I studies, there were no clinically relevant or apparent dose-related post-treatment changes in vital signs. Although transient changes in blood pressure, HR and body temperature were noted at isolated time points for some subjects, none of these findings were judged to be clinically significant by the Investigator.

Electrocardiogram Data

In 8 of the Phase I studies in healthy subjects there were no apparent treatment or dose-related trends in the 12-lead ECG parameters and no clinically important findings in the morphology of the 12-lead ECG for individual subjects. However, in 1 study (Study 101), prolongations in QT interval corrected for QTcB of >60 ms occurred in 2 subjects in the 1 mg fasted dose group; yet, no subjects had prolonged QTcB intervals >450 ms. Three subjects in the 1 mg fasted dose group and 1 subject in the 5 mg fasted dose group had prolonged QT intervals corrected for QTcF (>450 to 480 ms) although no subjects had a QTcF interval >480 ms. All episodes of QTcF >450 ms occurred at HRs <50 bpm.

Subjects with Gout or Asymptomatic Hyperuricemia

Information on clinical safety findings in subjects with gout or asymptomatic hyperuricemia is available in the IB [1].

